**EFFECT OF LIPID INTAKE ON DIRECT HYPERBILIRUBINEMIA IN LATE PRETERM
AND TERM INFANTS WITH GASTROINTESTINAL SURGICAL PROBLEMS**

NCT01555957

I. PURPOSE OF THE STUDY AND BACKGROUND

The purpose of the study is to establish a cause and effect relationship between lipid intake and the incidence of direct hyperbilirubinemia (cholestasis) in late preterm and term infants with major gastro-intestinal (GI) surgical disorders such as gastroschisis, omphalocele, volvulus, TE fistula, duodenal atresia, jejunal atresia, ileal atresia, Hirschsprung's disease, anorectal malformation, intestinal obstruction and GI perforations requiring surgery. Infants with major GI surgical disorders as mentioned above will be randomized to receive 1gm/kg/day or 2gm/kg/day of 20% intralipids within the first 72 hours after birth. The study is not open to all surgical infants because infants with other surgical problems can be fed enterally within few days after surgery and usually do not require TPN for prolong periods (>2 weeks). Also infants with major GI surgical disorders have similar clinical course, undergo similar type of operative procedures, and have similar complications thus eliminating potential confounding factors. The primary outcome measure is the incidence rate of parenteral nutrition associated cholestasis (PNAC). PNAC will be defined as serum direct bilirubin $\geq 2\text{mg/dl}$ in the absence of other known causes of direct hyperbilirubinemia as described under exclusion criteria.

II. BACKGROUND AND JUSTIFICATION:

Since its introduction in the late 1960s, total parenteral nutrition (TPN) has established itself as an effective mode for parenteral hyperalimentation in patients with acute or chronic intestinal failure. Out of the many complications of parenteral nutrition, the most common is the cholestasis often referred to as Parenteral Nutrition Associated Cholestasis (PNAC). PNAC is defined clinically using

direct bilirubin as an index measure in the absence of other known causes of direct hyperbilirubinemia (see exclusion criteria). The reported incidence of PNAC in neonates is as high as 84%. [1, 2]

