PNAC was first described by Peden and colleagues [3] and has long been recognized as a major cause of morbidity and mortality in neonates and infants. [4, 5] PNAC can be associated with liver dysfunction, cirrhosis, and hepatic carcinoma. The proposed mechanisms that could explain cholestasis caused by the total parenteral nutrition are multifactorial. The major mechanisms include hemodynamic modifications within the biliary system caused by parenteral administration of nutrients, bile stasis resulting from decreased stimulation of gastrointestinal hormones in the absence of any enteral intake, direct toxic effects of TPN components, premature biliary system, and bacterial overgrowth leading to overproduction of deconjugated bile acids. Very few observational studies done earlier have looked at the association of PNAC with various nutritional components of TPN. The findings of these studies indicate that PNAC could be associated with increased duration of TPN [6, 7] with almost all infants developing PNAC by 6 weeks on TPN [8,9,10], higher intake of amino acids [11], higher intake of dextrose, intake of trace elements like aluminium [12], copper and manganese [13], and cumulative amount of intravenous lipid intake[14]. Several preventive trials have been conducted in neonates involving the use of different amounts of protein intake or the use of choleretic medications in order to prevent cholestasis. Vileisis and colleagues [11] did not find any difference in the incidence of PNAC when they compared amino acids intake of 2.3gm/kg/day vs. 3.6 gm/kg/day. Their findings were reciprocated by Clark and colleagues [15] who found no difference in the incidence of PNAC when comparing amino acids supplementation of 2.5 vs. 3.5gm/kg/day. Similarly, the use of both cholecystokinin (CCK) [16], and ursodeoxycholic acid [17] failed to prevent the development of PNAC. Majority of these preventive trials performed in neonates defined PNAC as direct bilirubin ≥ 2 mg/dL after two weeks on PN [9, 11, 21]. Because these preventive trials failed to identify any

preventive therapy, there is a need to identify alternative ways to prevent PNAC in high-risk infants.

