Recent literature including our finding from an observational study suggests that cumulative lipid intake may be associated with PNAC in high-risk infants with GI surgical disorders. The side effects of intravenous lipid infusions on the hepato-biliary system was first suggested in animal studies in 1993 when La Scala et al. described that the addition of lipids increases TPN associated cholestasis in rats [18]. Haynes et al. in 2002 published a series of hepatic pathology and described dose dependent hepatic changes with prolonged administration of lipid in premature baboons which included steatosis, cholestasis, and proliferation of bile ducts [19]. Since then few observational studies in neonates have been performed and demonstrated that lipid intake is associated with PNAC. [7, 11] However, a cause and effect relationship between lipid intake and PNAC has not been established using a well-designed randomized clinical trial. We hypothesize that increased cumulative amount of lipid intake causes PNAC in late preterm and term neonates with major GI surgical disorders. Our objective is to evaluate the effect of cumulative amount of lipid intake on the incidence of PNAC in this vulnerable population.

III. CHARACTERISTICS OF THE RESEARCH POPULATION

1. **Number of Subjects:** This is a prospective randomized clinical trial involving 40 neonates with major GI surgical disorders requiring surgery.
2. **Gender, Age, Race, and Ethnicity:** The University of Rochester Medical Center (URMC) is a tertiary care center and consists of a 52 bed Neonatal Intensive Care Unit. Annually, ~25 infants with major GI surgical disorders are admitted to the URMC. The NICU population is approximately 52%

male with a racial distribution of 64% White, 32% African-American, 2% Asian, and 2% other. The ethnic distribution is 75% non-Hispanic. The gender, race, and ethnicity distribution of this prospective study is expected to follow the distribution of the NICU population.

3. **Inclusion Criteria:** All neonates \geq 34 weeks gestational age with major GI surgical disorders (gastroschisis, omphalocele, volvulus, trachea-esophageal fistula, duodenal atresia, jejunal atresia, ileal atresia, hirschsprung's disease, anorectal malformation, intestinal obstruction, and GI perforations) requiring surgery admitted to our NICU within first 72 hours will be eligible for this study.

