4. **Exclusion Criteria:** Neonates with the following condition will be excluded: 1) If does not need TPN by 72 hours; 2) Direct hyperbilirubinemia within the first 72 hours after birth; 3) TORCH infections (Toxoplasmosis, CMV, Herpes, Rubella, HIV, etc); 4) Biliary tract disorders leading to direct hyperbilirubinemia; 5) Known metabolic disorders that may be associated with direct hyperbilirubinemia- such as Galactosemia, α -1 antitrypsin deficiency, etc.

IV. METHODS AND PROCEDURES

a) Study Design: This is a prospective randomized controlled trial s planned in order to evaluate the incidence rate of PNAC between 1gm/kg/day of 20% intralipid and 2 gm/kg/day of 20% intralipid in high-risk neonates \geq 34 weeks gestational age (GA). PNAC will be defined as serum direct bilirubin \geq 2mg/dl in the absence of other known causes of direct hyperbilirubinemia as described in the exclusion criteria.

b) Screening: All neonates \geq 34 weeks GA and admitted to the NICU at URMC with major GI surgical disorders will be screened for study criteria within 72 hours after birth. Infants will be

identified by a designated investigator with regularly scheduled screening of admissions, GA, postnatal days and admission diagnosis. Screening will take place on an ongoing basis and not less than 3 times per week. The screening log will include GA, postnatal days, and type of GI surgical disorders, and whether or not the infant was enrolled in the study. If not enrolled, the reason will be recorded. The number and demographic characteristics of eligible subjects not included will be collected to assess the representation of the sample of subjects included.

- c) Enrollment and Consent:** Families will be approached by one of the investigator as soon as possible after eligibility is ascertained to allow sufficient time for the family to ask questions about the study. Parental consent may be obtained any time during the first 72 hours after birth. Consent will be documented on an IRB approved consent form. Each subject will be assigned a unique study identification number by the investigator after consent is obtained.
- d) Pre-randomization:** Once the infant is enrolled in the study, one of the investigators will notify the Research Pharmacist (RP) by telephone call during working hours (8AM-5PM) for registration and randomization. Information on weight of the infant will be provided to the RP for accurate dosing of intravenous lipid on each day.

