- e) Registration:** A log sheet of subjects registered with their names, study ID numbers, medical record number, dates of birth, and dates of randomization will be kept by the RP
- f) Randomization** will be to two arms: 1g/kg/day intravenous lipid or 2 g/kg/day for 6 weeks or until develops direct bilirubin \geq 2mg/dl (in the absence of sepsis) or reaches enteral feeds and no longer requires parenteral nutrition. A block randomization with 8 subjects in each block will be performed. Study group assignments will be made by the RP with the use of a randomization scheme provided by the biostatistician. The assignment will be 1:1 ratio.

g) Route, Frequency, and Duration: The lipids will be given intravenously every day as per the standard of care for 6 weeks or until reach one of the study end points (reach enteral feeds and no longer require parenteral nutrition or has direct bilirubin ≥ 2 mg/dl in the absence of sepsis). All enrolled infants including those randomized to 2 gm/kg/day intravenous lipid will be started at 1 gm/kg/day of intravenous lipids as per the standard of care on day 2 after birth. The procedures for titrating subjects randomized to the higher dose will be consistent with standard procedures. The daily intravenous lipid intake will be increased to 2 gm/kg/day in those randomized to 2 gm/kg/day. The amount of proteins and glucose will be ordered as per the unit policy and at the discretion of the attending neonatologist.

h) Dose Adjustments: Daily assessment of the weight will be performed by the investigator and will be reported to the RP for appropriate adjustment to the dosing of the intravenous lipid. Each day, the RP will inform the clinical care team of volume of intravenous lipid to be infused over the day. The clinical care team will complete the request in the E-record using the information provided by the investigator or the RP.

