VI. SAMPLE SIZE CALCULATION: Assuming a 4-week median follow-up time and an incidence rate of 40% for 6 weeks in control group, a two-sided log rank test with an overall sample size of 40 subjects (20 per group) achieves 80.0% power at a 0.050 significance level to detect a hazard ratio of 3.6.

Power	Incidence Rate	N Control	N Study	Haz Ratio (HR)
0.8	40%	20	20	3.6
0.8	50%	20	20	3.26
0.8	60%	20	20	3.02

Kaplan-Meier (KM) estimates of survival function will be provided and compared between groups. Log-rank test will also be used to compare time to endpoint. Cox proportional hazards model will be fitted after controlling for covariates which are found to be imbalanced in preliminary analysis. Estimate of hazard ratio and associated confidence interval will be obtained.

VII. DATA ANALYSES AND MONITORING:

a) **Randomization:** Upon successful completion of necessary screening assessments and being confirmed to be eligible by the investigator, subjects will be randomized in 1:1 ratio to two groups: 1) 1 g/kg/day intravenous lipid and 2) 2 g/kg/day intravenous lipid. Each subject will be assigned a unique sequential subject number for identification throughout the entire course of the study. The subject number will not be reused for any other participant in the study. Subjects who are discontinued or withdrawn from the study prior to randomization will be replaced. In addition, subjects who are identified to have direct hyperbilirubinemia from causes other than parenteral nutrition or did not require parenteral nutrition for more than 2 weeks will be considered screen failure and will also be replaced. We anticipate a total number of 52 subjects to participate in the study to complete the study on 40 subjects. During the study, the treatment assignments will be available only to the RP.

c) **Samples for Analysis:** The “Intent-to-Treat” sample includes all subjects who are randomized into the study. Subjects will be grouped according to the treatment to which they are randomized.

d) Statistical Analyses:

General statistical Considerations:

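### Infants can be called screen failures and replaced on facts known only after randomisation, which conflicts with the intent-to-treat and censoring rules if they leave the analysis

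*Combined protocol and SAP*

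**What the plan says.** All places are in the combined protocol and SAP.

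- **Timing.** Section I has infants "randomized to receive 1gm/kg/day or 2gm/kg/day of 20% intralipids within the first 72 hours after birth". IV.c places consent in the same 72 hours. The only exclusion concerning PN need (III.4) is "If does not need TPN by 72 hours".
- **Replacement.** VII.a first replaces infants who withdraw before randomisation. It then adds a second group: infants with direct hyperbilirubinemia from a cause other than PN, and infants who "did not require parenteral nutrition for more than 2 weeks will be considered screen failure and will also be replaced". It expects 52 participants in order to finish with 40.
- **Analysis sample.** VII.c names one sample, intent-to-treat, made up of every randomised infant in the assigned arm.
- **Short PN.** IV.g ends the randomised lipid at 6 weeks or when infants "reach enteral feeds and no longer require parenteral nutrition or has direct bilirubin ≥ 2 mg/dl in the absence of sepsis", with no minimum PN duration. VII.d censors infants who reach full enteral feeds before 6 weeks, again with no 2-week floor.
- **Late-found exclusions.** VII.d sets infants later found to meet an exclusion criterion aside for a separate analysis.
- **Tests.** The log-rank and Cox analyses are described in VI and again in VII.d. Neither description says which sample they use.

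**The concern.** A screen failure is normally an infant who never reaches randomisation. Here the label can be applied about two weeks after randomisation, on the basis of something that happened on study treatment. An infant off PN on day 10 is at once a member of the intent-to-treat sample, a censored observation and a replaced screen failure.

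Three primary sets can be defended from the text: all randomised infants; all randomised infants minus those analysed separately; or the 40 with PN beyond 2 weeks and no other cause. The choice could be made after the data are seen.

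The last two sets select on post-randomisation facts. The other-cause limb acts only on infants whose direct bilirubin has risen, which is a component of the primary outcome. If PN duration or attribution of cause depended on arm, the comparison would no longer be fully randomised. VII.a reserves knowledge of the assignments to the research pharmacist (RP), yet IV.h says "Each day, the RP will inform the clinical care team of volume of intravenous lipid to be infused over the day", so such dependence cannot be ruled out.

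**Working it through.** **1. The plan's own power figure.** Inputs from VI: 20 per arm, two-sided 0.05, 40% incidence at 6 weeks in control, HR 3.6.

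- Expected events without early censoring: 20 × 0.40 + 20 × (1 − 0.6^3.6) = 24.8. Freedman power: Φ(√24.8 × (3.6 − 1)/(3.6 + 1) − 1.96) = 80.4%.
- With 4 weeks of follow-up for everyone and constant hazards: 19.9 events. Schoenfeld power: Φ(√19.9 × ln(3.6)/2 − 1.96) = 81.5%.

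The stated 80% reproduces. The other two rows of the table (HR 3.26 and 3.02) also come out within 1 point of 80% by either route.

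**2. How many infants are affected.** 52 − 40 = 12, and 12/52 = 23.1%. This is an upper bound, because VII.a does not split the 12 into losses before and after randomisation. If, for illustration, 6 left before randomisation, the share would be 6/46 = 13.0%.

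**3. Effect of the choice of set.** Log-rank simulation with control hazard −ln(0.6)/6 = 0.0851 per week, HR 3.6 and 1:1 allocation. The following are assumptions, not plan figures: constant hazards; PN duration independent of arm; censoring when PN ends; all 12 of 52 counted as short PN, uniform on 0.5 to 2 weeks (in the 46-infant row, 6 of 46). The remaining infants have PN durations of either

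- A: uniform on 2 to 6 weeks; or
- B: uniform on 2 to 7.71 weeks, capped at 6, which makes the median 4.0 weeks over all randomised infants.

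| Set analysed | Power, A | Power, B |
|---|---|---|
| 52 randomised, all kept | 82% | 85% |
| 52 randomised, short PN dropped | 77% | 81% |
| 46 randomised with 13% short PN, all kept | 80% | 84% |
| 40 infants, all with PN over 2 weeks | 78% | 82% |
| 40 randomised with 23% short PN, all kept | 71% | 75% |

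With HR 1, the rejection rate is 4.9 to 5.2% whether short-PN infants are kept or dropped. The median estimated HR under A is 3.65 either way. Lognormal durations (median 4 weeks, 23% at 2 weeks or less) give 85%, 82% and 75% for the first, second and last rows.

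**4. Events lost by dropping short-PN infants.** Under A, 2.5 of 21.9. Under the figures in IV.m (PNAC after a cumulative 55 g/kg, SD 15, treated as normal, with the 2 g arm assumed to be at full dose from day 3), about 0.05 of 10.4, and power is 96% kept or dropped.

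**5. The 4-week median in VI.** Under A, the median PN duration is 4.0 weeks among infants with PN over 2 weeks, but 2 + 4 × (0.5 − 0.231)/0.769 = 3.4 weeks over all 52. The sample-size input therefore depends on which set is meant.

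**The case against.** The strongest reply is that intent-to-treat already governs. VII.c is headed as the analysis sample, directly precedes the statistical methods and names only one set. Replacement is a recruitment term, no sentence removes a short-PN infant, and the censoring rule keeps such infants. IV.m adds that the 40 already allows for variable TPN duration. This is a fair reading, and it rules out saying that the plan names no sample. It does not settle the matter: the screen-failure label and the aim of finishing with 40 out of 52 point the other way, and no sentence ties the tests to VII.c.

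Second, the other-cause limb is largely covered. Sections I and IV.a define other causes through the exclusion criteria, and VII.d says what happens to infants who meet them. The listed conditions are mostly congenital, so setting those infants aside is less worrying than an exclusion that depends on treatment. That is right, but VII.d's rule still takes randomised infants out of an all-randomised sample, and short PN is not an exclusion criterion, so the rule does not reach those infants.

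Third, the 2-week rule reflects the population the trial wants. Section II notes that most earlier prevention trials "defined PNAC as direct bilirubin ≥ 2 mg/dL after two weeks on PN". That justifies an interest in the subset, but not selecting it after randomisation for the primary comparison.

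A reader might also infer that an infant whose bilirubin rises during sepsis becomes a screen failure. The documents do not support this. Sepsis is not among the exclusion criteria that define other causes; IV.g and V only say that such a rise is not an endpoint.

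**Conclusion.** The concern holds as an inconsistency that should be fixed. VII.a's 2-week rule can operate only after randomisation. If it or the separate analysis in VII.d removes infants, it contradicts VII.c, and for short-PN infants it also contradicts the censoring rule. Removal is implied, not stated.

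The demonstrated size is modest: about 4 to 5 points of power under constant hazards, and essentially nothing under the plan's cumulative-dose figures. These results rest on assumed PN durations independent of arm and on counting all 12 replacements as short PN.

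Two stronger inferences are tempting. The first is that the comparison is biased or its type I error inflated. The simulations show no inflation when duration is independent of arm, and the documents give no evidence of dependence; the care team's knowledge of the lipid volume makes it possible, no more. The second is that the stated 80% power is wrong. It reproduces. The 71 to 75% figure applies only if 40 are randomised, 23% of them have short PN and all are kept, which is a question about the randomised number rather than an error in the calculation.

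**What to change.** 1. **VII.a:** limit screen failure to infants not yet randomised. State that any infant recruited as a replacement after randomisation is additional and removes no one from the analysis.
2. **VII.c:** state that the primary log-rank and Cox analyses use all randomised infants in their assigned arm, with short-PN infants kept and censored under the existing full-feeds rule in VII.d.
3. **VII.d:** keep infants later found to meet an exclusion criterion, or to have another cause, in the primary set under one stated rule that is the same in both arms (for example, censored on the date of that finding). Turn the present separate analysis into a sensitivity analysis.
4. **VII.d:** report the subset with PN over 2 weeks and no other cause as a sensitivity analysis, and show the excluded infants by arm.
5. **VI:** say whether 40 or 52 infants are to be randomised, which set the 4-week median describes, and the power for that number.

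The cost is text in four places and two sensitivity analyses. No extra enrolment or sampling is required; restating the power is enough. The drawbacks are that short-exposure infants add little information, and that the restated power may be less favourable than 80%: about 71 to 75% under the assumed durations if only 40 are randomised.

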 - 2) Our hypothesis is that the development of PNAC is causally related to the cumulative lipid intake, however, protein and glucose intake may modify the association between lipid intake and PNAC. In addition, sepsis and prematurity are confounding risk factors. The sample size calculated ($n=40$) to evaluate the outcome measure (or the adverse event) accounts for the variable duration of the TPN (cumulative lipid intake) and presence of confounding risk factors. Therefore, meaningful statistical analysis is not possible with an interim analysis of less than 40 subjects.
 - 3) As suggested by our observational study, a mean cumulative dose of 55gm/kg (SD 15) of intravenous lipid is required before the development of PNAC in late preterm and term

infants. Thus, it is expected that an infant on 1gm/kg/day of intravenous lipid arm will take ~ 55 days to develop PNAC. Therefore, considering the fact that TPN intake will often be less than 42 days among study subjects, not all infants in either group are expected to develop PNAC. PNAC, the study outcome, as defined for the purpose of the study, is the earliest when any medications are used to treat PNAC as per the standard of care. Severe PNAC is defined when direct bilirubin concentration is > 10 mg/dL and is very rare. The randomization of intravenous lipid intake will be stopped long before severe PNAC may be seen among enrolled subjects.

- 4) Performing interim analyses will require more stringent significance level which will increase the sample size required to perform the study. This is a pilot study performed as part of fellow's project for which 40 subjects are required for meaningful analysis of outcome (or adverse event)
- 5) This study has been designed as a block randomization with each block having 8 subjects with 1:1 assignment, so even if all enrolled infants were to develop PNAC, it will suggest that there is no difference between the two groups and there is no causal association between intravenous lipid intake and cholestasis.

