Because of reasons mentioned even if the first 20 subjects (50%) hit the direct bilirubin endpoint, interim analysis is unlikely to allow meaningful analysis of the causation between lipid intake and the outcome measure (or adverse event) as provided in the protocol. In other words, it is unlikely to reach adjusted statistical significance required for interim analyses. Thus, since the outcome measure and the adverse event are the same and the sample size required to evaluate the association (or the adverse event) controlling for other factors is 40, no interim analysis and stopping rules were considered for this pilot study. For trial management, the investigation team will track enrollment and protocol compliance and review every 3 months.

V. DATA COLLECTION: The baseline data on demographics and clinical factors (antenatal and postnatal) before randomization on each subject will be collected. Similarly, data on clinical factors will be collected during the 6 week study period or until the subject is receiving intravenous lipid as per

randomization or until the subject develops PNAC (direct bilirubin ≥ 2 mg/dl in the absence of concurrent infection).

The information on TPN components, specifically amount of lipid, protein, and glucose intake on each day will be prospectively collected using pharmacy and TPN records. Information on cumulative amount of lipid intake, cumulative amount of protein intake, and cumulative amount of glucose intake will be determined for all enrolled subjects. The additional information that will be collected is duration (days) of TPN, use of trace elements, duration (days) of NPO, type of enteral feeds (maternal breast milk vs. Formula) duration (days) of antibiotic use, onset and duration of choleric medications, sepsis defined as blood culture positivity or clinical signs and symptoms of sepsis with the use of antibiotics for > 3 days, day of life when the infant reaches an enteral intake of 120 ml/kg/day, duration (days) of mechanical ventilation, duration of CPAP, duration of oxygen supplementation, and amount of erythrocyte transfusions during the study period. However, use of choleric medications and discontinuation of trace elements from the TPN is not expected during the study period based on the unit policy as delineated earlier.

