All statistical analyses will be conducted using Version 10 of the SAS System for Windows (Copyright © 2002-2003 SAS Institute Inc., Cary, NC, USA.) by a biostatistician. Descriptive statistics will be used to summarize outcomes by treatment groups. For continuous variables, descriptive statistics will include the mean, median, standard deviation, minimum, maximum, number of available observations, and number of missing observations. For discrete variables, descriptive statistics will include frequencies and percentages, number of available observations and numbers of missing observations.

We will determine whether there are important baseline differences between the two groups despite randomization with respect to participant characteristics (e.g., gender, race/ethnicity, GA at birth, SGA[<10th percentile]). If any important differences are found, the primary analyses will be repeated after statistically adjusting for these differences. If distributional assumptions associated with a particular statistical procedure are violated, appropriate transformations will be made or non-parametric alternatives will be used (e.g., Wilcoxon rank sum tests in place of two-sample t-tests). Infants enrolled but subsequently found to meet exclusion criteria will be analyzed separately.

The incidence rate of PNAC will be compared between the 2 groups using Kaplan Meier curves. Subjects who reach full enteral feeds before 6 weeks of study period will be censored. Kaplan-Meier (KM) estimates of survival function will be provided and compared between groups. Log-rank test will also be used to compare time to endpoint. Cox proportional hazards model will be fitted after controlling for covariates which are found to be imbalanced in preliminary analysis. Estimate of hazard ratio and associated confidence interval will be obtained.

The potential confounders are sepsis, use of choleric medications and trace elements. Incidence of nosocomial sepsis has decreased remarkably over the last few years in our unit and with

randomization we do not anticipate significant group differences in the incidence of sepsis. The use of choleric medications and discontinuation of trace elements should occur after the development of primary outcome as per the unit policy and therefore these factors are unlikely to confound the relationship between the lipid intake and PNAC.

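### The only hazard ratio and CI the plan promises come from a Cox model whose covariates are picked by an undefined imbalance rule, and n=40 is wrongly said to control for confounders

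*Combined protocol and SAP*

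**What the plan says.** Section VI sizes the trial on "a two-sided log rank test with an overall sample size of 40 subjects (20 per group"), with no covariates. Sections VI and VII.d then list Kaplan-Meier curves, "Log-rank test will also be used to compare time to endpoint", and "Cox proportional hazards model will be fitted after controlling for covariates which are found to be imbalanced in preliminary analysis". The next sentence is "Estimate of hazard ratio and associated confidence interval will be obtained". That is the only effect estimate with an interval in the plan, and the Cox model just described is the only one named.

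A second rule stands earlier in VII.d. Baseline characteristics are compared (sex, race/ethnicity, GA at birth and SGA are given as examples), and "If any important differences are found, the primary analyses will be repeated after statistically adjusting for these differences". Neither rule gives a test, a threshold or a closed list of covariates.

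In IV.m (Data Safety Monitoring), reason 2 states that the sample size of 40 "accounts for the variable duration of the TPN (cumulative lipid intake) and presence of confounding risk factors". It continues: "Therefore, meaningful statistical analysis is not possible with an interim analysis of less than 40 subjects". The closing paragraph of IV.m repeats that "the sample size required to evaluate the association (or the adverse event) controlling for other factors is 40".

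**The concern.** Two analysts following VII.d could report different HRs and CIs from the same 40 infants, because one sees an imbalance where the other does not. In a correctly randomised trial every imbalance is due to chance, so this rule adds covariates whether or not they predict cholestasis, and leaves out a strong predictor that happens to be balanced. In a small pilot the HR and CI are what a later trial would be planned from.

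The IV.m statements are a separate matter. If the calculation makes no allowance for confounders, a sample size described as controlling for them is misdescribed, and a reason given for having no interim analysis lacks support.

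**Working it through.** **1. The plan's own power figure.** Inputs from section VI: two-sided 5% test, 20 per group, control incidence p at 6 weeks, 4-week median follow-up. Take a constant control hazard h = -ln(1-p)/6 per week and follow every infant for 4 weeks. Expected events are D = 20[(1-exp(-4h)) + (1-exp(-4h·HR))]. Schoenfeld power is Φ(√D/2 · ln HR - 1.96).

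First row: h = 0.5108/6 = 0.0851; event probabilities 0.289 and 0.707; D = 20 × 0.995 = 19.9; power = Φ(2.231 × 1.281 - 1.96) = Φ(0.897) = 81.5%.

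| Control incidence | HR | Events | Power |
|---|---|---|---|
| 40% | 3.6 | 19.9 | 81.5% |
| 50% | 3.26 | 23.0 | 80.8% |
| 60% | 3.02 | 26.0 | 80.4% |

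Freedman's formula with all 6 weeks also fits (24.8, 27.9 and 30.7 events; 80.4, 80.0 and 79.6%). The documents do not show which was used, but neither needs a covariate term. An allowance would leave a trace: if covariates explained an assumed 10% of the variance of treatment, N would be 40/(1-0.10) = 44.4, that is 45. The stated 40 is the figure for no allowance.

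**2. How often the rule triggers, by cut-off.** Exact binomial, 20 v 20, for the four characteristics in VII.d. Male 52% and White 64% come from section III.2. SGA 10% is assumed from its definition. GA is treated as continuous, with standardised differences of 0.2, 0.4 and 0.6 standing for 10, 20 and 30 points, or a t-test.

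| Trigger | Male | White | SGA | GA | At least one |
|---|---|---|---|---|---|
| ≥10 points (2 infants) | 63.6% | 62.1% | 41.7% | 53.1% | 96% |
| ≥20 points (4 infants) | 26.8% | 24.8% | 6.3% | 21.4% | 59% |
| ≥30 points (6 infants) | 8.0% | 6.9% | 0.4% | 6.5% | 20% |
| p<0.05 | 4.3% | 5.2% | 3.9% | 5.0% | 17% |

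The last column is 1 minus the product of the four non-trigger probabilities. For 10 points: 1 - 0.364 × 0.379 × 0.583 × 0.469 = 0.96. That rule enters 0.636 + 0.621 + 0.417 + 0.531 = 2.2 covariates on average.

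**3. Effect on the reported HR and CI.** Simulated trials at true HR 3.6, 20 per arm, control incidence 40% at 6 weeks. Assumed: GA uniform over 34-40 weeks, parenteral nutrition lasting uniformly 2-6 weeks (median 4), constant hazards and continuous event times. Each trial is analysed under every cut-off in the set. Ranges are across repeated runs.

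| Cut-offs compared | HR differs >10% | HR differs >25% | CI verdict on 1 differs | Same, if GA carries HR 1.3 per week (assumed) |
|---|---|---|---|---|
| All four | 48-51% | 19-21% | 7.8-8.5% | 11.7-12.2% |
| Without the 10-point rule | 22% | 8% | 3.2-4.9% | 5.7% |
| 30 points v p<0.05 | 5-6% | 2% | 0.8-1.7% | 1.1% |

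The first three result columns assume that no covariate is prognostic.

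**4. Type I error.** With no treatment effect, likelihood-ratio rejection was 5.1-6.7% under the imbalance rules and 5.0-5.9% for unadjusted Cox; the log-rank test rejected in 4.8-5.5%.

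**5. An arm without events.** IV.m reason 3 puts the mean cumulative dose before cholestasis at 55 g/kg (SD 15). At 1 g/kg/day, 42 days give at most 42 g/kg, so events in that arm may be few. Simulating that model, one set-up gave a finite Cox HR in 59% of trials; another gave no low-dose-arm events in 31%.

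**The case against.** The strongest reply is about size. Ten points at 20 per arm is two infants, and nothing in VII.d suggests a biostatistician would call that important. This stands: the 96% trigger rate and the 8-12% both depend on that rule, and without it the figures are modest. The shifts are also small against the trial's own precision. With a standard error of log HR near 0.5, a 10% change in HR is about 0.2 standard errors and a 25% change about 0.45.

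A reader might infer that the plan provides no unadjusted analysis at all. The wording does not support that: an analysis that is repeated with adjustment implies that an unadjusted one came first, and the unadjusted log-rank test is the one that was sized. What remains is narrower: no unadjusted Cox HR is named, and the sentence that yields the HR and CI follows the adjusted model.

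Deleting the repeat is a preference, not a necessity; a labelled exploratory analysis serves as well. The case for GA is also limited. Its prognostic strength is unknown from the documents and may be small with entry restricted to 34 weeks or more. An unadjusted and a GA-adjusted CI would themselves disagree on excluding 1 in 4.5-11% of trials at HR 3.6, so the plan must say which governs. Finally, bilirubin is measured weekly (IV.k), and the simulations do not model the resulting ties.

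**Conclusion.** The concern holds in a limited form. Observed imbalance selects the covariates behind the only HR and CI the plan promises, by a rule that two analysts could apply differently. Its effect on whether the CI excludes 1 runs from about 1-2% of trials between strict cut-offs, through 3-6%, to 8-12% if a two-infant difference counts. These figures rest on the assumed GA distribution, SGA rate, GA effect and censoring.

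Three stronger readings are tempting and not supported. The log-rank p-value does not depend on the cut-off, because that test has no covariates. A fixed imbalance rule does not materially inflate type I error. And n=40 is not wrong: all three rows of the section VI table reproduce.

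What is wrong in IV.m is the description. The calculation reflects duration of parenteral nutrition only through the 4-week median follow-up, and confounders not at all. The confounder statement therefore cannot support the decision against an interim analysis. It is one of five listed reasons, and this point does not bear on the other four. The changes should be made, but they alter neither the sample size nor the primary test.

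**What to change.** (a) In VI and VII.d, replace the Cox sentence with: *The primary test is the unadjusted two-sided log-rank test at 5%. The unadjusted Cox HR with 95% CI is the reported effect. Beside it, a supportive HR with 95% CI is given from a Cox model with treatment and GA at birth (continuous, in weeks). Only variables measured before randomisation are entered, and none is added to or removed from these two models because of observed imbalance. If an arm has no events, a profile-likelihood or Firth-penalised HR and CI is reported with the Kaplan-Meier estimates.* Choose one of those two methods beforehand. GA is suitable because IV.m names prematurity as a risk factor, VII.d lists GA, and it is recorded at screening (IV.b). Sepsis, also named in IV.m, can arise after randomisation.

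(b) In VII.d, keep the baseline comparison as description. Label any further adjustment for an observed imbalance exploratory, and state that it does not replace the reported HR. Deleting the repeat is optional.

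(c) In IV.m, reason 2 and the closing paragraph, replace the confounder statements with: *n=40 is based on an unadjusted log-rank test with a 4-week median follow-up and makes no allowance for covariates.* Drop the confounder statement as a reason for having no interim analysis.

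The cost is wording; sample size and data collection do not change. The supportive model spends one extra term on about 20 events at the design HR. In simulation its likelihood-ratio type I error was 5.5-6.1%, and a Wald test under different assumptions gave 3.6-4.4%. Fixing GA costs almost no power if it is not prognostic (78.2% to 77.9%) and gains some if it carries an assumed HR of 1.3 per week (71.9% to 76.4%), but only for the supportive estimate. A chance imbalance in sex, race or SGA would be shown but not adjusted for in the reported HR.
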